- f) For other kidney related measures (e.g., ketones, bilirubin, WBC, RBC, bacteria, crystals), repeat, but no need to discontinue even if present on repeat, since unlikely to be D-serine related. Manage in consultation with medical specialist.
- g) Contaminated samples (hemolyzed/non-clean catch) will be repeated.

In addition

A subject will not receive any further doses of the study drug should any of the following events occur:

- Any serious adverse event. If drug relationship can be ruled out (e.g., hospitalization due to traumatic injury), no decisions will be taken for the study as a whole.
- Any other physical examination finding, change in vital signs, adverse event, or laboratory abnormality that in the opinion of the Investigator would cause an excessive risk if the subject continued the study.
- A CGI-improvement (CGI-I) score of 6 or 7
- Positive urine pregnancy test at any visit

Blood and other Biological Samples

Describe how the sample will be used and indicate, when relevant, the amount of the sample. The IRB wants to know that the sample is sufficient for the purposes of the study, but that sampling is limited to what is minimally necessary.

If you've indicated that you intend to store a sample for future use, indicate where the sample will be stored, how long the sample will be stored, and to what purposes the sample will eventually be put. Check the IRB website at <http://irb.nyspi.org/irbdnn/Policies/GeneticResearch/tabid/96/Default.aspx> for specific guidance and additional information about future use of DNA samples.

A total of up to 200 mL of blood (equal to 13.5 tablespoons) will be drawn during the entire study on different days, no more than one tablespoon at a time. Blood will be drawn for safety assessments and for pharmacokinetic sampling.

Assessment Instruments

List all assessment instruments, indicate who will administer them, and provide an estimate the duration of each. The IRB wants to know that assessments instruments are appropriate measures for the purposes of the study and are no more burdensome than is necessary. The IRB will consider the burden of assessment instruments (in terms of time, sensitivity of material, etc.) in the risk/benefit analysis. Please attach copies or otherwise provide all non-standard instruments.

Electrophysiology: **2-3** hours

MCCB: 1 hour

CGI-S/CGI-S: 5 minutes

SCID: 1 hour

PANSS: 30 minutes

C-SSRS ratings:10 minutes

Auditory and social cognition: 2-3 hours. In particular, auditory cognition is defined as the HVLT and letter number sequence test of the MCCB. In all, the ratings visit is expected to take 3-4 hours

Research Related Delay to Treatment

Research involving participants who are in need of treatment invariably involves delay to care, and this delay is associated with risk. Scheduling of procedures must be carefully organized to minimize delay. Other delay must involve only that minimally necessary to accomplish the aims of the research while respecting subject well-being and safety. Describe the delay, by virtue of research participation in this study, before a participant can receive treatment of known efficacy or standard care routinely offered in the community.

No. All subjects will be offered four months of free treatment after the study.

Clinical Treatment Alternatives

Describe what other treatment or assessment options are available to subjects who do not participate in research.

There are currently no FDA-approved treatments for cognitive deficits in patients with schizophrenia. Therefore, no proven treatment will be withheld from subjects. There are behavioral therapies such as Cognitive Remediation Therapy that may address cognitive deficits.

Risks/Discomforts/Inconveniences

"Risk" is a broad term used to convey the potential for harm, burden, and inconvenience related to research participation. Use this section to provide a comprehensive description of foreseeable physical, psychological, social, interpersonal, and economic risks introduced by the research. Include the source of the information. Consider both the probability and magnitude of harm and its impact. Describe the foreseeable harms associated with the research (untoward effects of a medication) and those related to delay to individualized treatment. Include data from the literature, and local data, if available, on risk rates and subject experiences with research procedures. Describe procedures in place to minimize risk. In general, please create a numbered list of risks/categories of risk, and in general put the list in the order of significance or level of risk, the most significant risks first followed by others.

Risks associated with D-serine

Please see the main grant application for a full description of D-serine safety, including animal studies and pharmacokinetics.

The PI has an active IND for D-serine (122821), specifically permitting use up to 120 mg/kg in this protocol.

D-serine is a naturally occurring amino acid that is present in high concentrations in the human brain. D-serine is cleared almost exclusively by the kidney.

The primary safety concern of D-serine is the potential for nephrotoxicity. Nephrotoxicity is a theoretical concern during D-serine treatment, as rats receiving D-serine experience a reversible acute tubular necrosis. When present, this toxicity leads to high levels of glucose and protein being present in the urine. This effect, however appears to be isolated to rats, in that other rodent species (e.g., mice) do not show similar sensitivity to D-serine, nor is toxicity observed in non-rodent species (e.g., rabbit, dog, monkey)²¹⁹. Further, toxic effects of D-serine, even in rats, are fully reversible even with continued D-serine treatment. The specific sensitivity of rats appears to be due to the presence of a D-serine transporter in rat kidney that actively reabsorbs D-serine from the urine, leading to buildup of high levels within the rat kidney. The presence of this transport mechanism is apparent from the low levels of D-serine in rat urine relative to that of other species, despite relatively similar serum levels.

In humans, there is no evidence of reabsorption of D-serine by the kidney. The safety of high dose D-serine in non-rat animal species has been further established as part of the safety reports provided to the FDA for my IND.

14 human trials have been published with D-serine (Table), including 431 subjects and treatment duration up to 16 weeks of daily dosing. 102 subjects received high dose (>30 mg/kg), including 16 patients at 120 mg/kg. Across all of the studies, only one subject was reported to have abnormal renal values related to D-serine treatment. The abnormality occurred in a subject receiving 4 weeks of the 120 mg/kg dose. Even at that dose, the abnormality was extremely mild in that it involved only an increase in protein (2+ by dipstick) without accompanying increase in glycosuria or change in creatinine level. The abnormal urinalysis values were observed 4 weeks following treatment onset, and fully resolved within a few days of stopping treatment.

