Study overview: Schizophrenia (Sz) is a major public health problem that affects ~1% of the population worldwide. Sz is associated with deficits in neurocognition¹⁻⁴ that represent a core feature of the disorder and that may precede illness onset⁶, and predict impaired psychosocial function^{7,8}. When comprehensive neurocognitive batteries are used, patients show deficits across a large variety of cognitive domains, suggesting widespread cortical involvement. In addition, Sz patients show reduced neuroplasticity in tasks designed to produce learning, leading to reduced ability to benefit from various forms of cognitive remediation⁹⁻¹¹. The effects of intervention strategies aimed at remediating neuroplasticity deficits, however, have been evaluated to only a limited degree. *Thus, remediating neuroplasticity is a rate-limiting first step prior to remediating cognition and overall function. Plasticity represents an unmet clinical need and a clinically relevant target. The goal of this NIMH sponsored two-site, two-phase R61-R33 study is to enhance efficacy and efficiency of auditory cognitive remediation by augmenting with D-serine.*

For both the R61 and R33 phase, we utilize the same neuroplasticity-based auditory remediation program which has demonstrated a dynamic, direct link between behavioral/neurophysiological plasticity and cognitive improvements.

The R61 phase is designed to assess whether D-serine has dose dependent target engagement over 3 sessions (1x week) of auditory remediation.

During the R61, we will confirm target engagement, pharmacodynamics, functional relationships and the optimal dose (80 vs. 100 vs. 120 mg/kg, IND: 122821) of D-serine treatment combined with 3 sessions of our auditory remediation program. *As previously, D-serine will be given 30 minutes before sessions, allowing for auditory remediation during peak serum levels and a pharmacodynamic assessment.* Successful completion of the R61 (go/no go) is defined by \geq moderate effect size change in auditory plasticity, MMN and θ -ITC, plus a moderate effect size correlation with functionally relevant cognitive measures ("auditory cognition": without safety issues).

In the R33, we directly evaluate functional improvement as an outcome, assessing the sustained effects of D-serine + 16 sessions (1x week) of the same auditory remediation program used in the R61.

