Direct evidence for D-serine enhancement of plasticity: In our preliminary study ([name] 2016), 21 Sz patients (44.0±11.5, 90% men) received three neuroplasticity-based remediation sessions separated by 1-week, paired with either D-serine 60 mg/kg or placebo, which were administered in an interleaved fashion across subjects. Analyses focused on effects of both initial and repeated D-serine administration. 13 Sz were studied in a double-blind randomized control design, with 8 additional Sz studied in an open label design to increase power for EEG analysis. Behavioral data are presented only from Sz subjects who participated in the blinded study, while EEG were analyzed from all subjects. D-Serine was given 30 minutes before sessions to allow for training at peak levels⁹.

On their initial treatment day, there was no significant between group difference in plasticity ($p=0.96$). Change over repeated D-serine administration was then evaluated by comparing effects of treatment order in subjects who received either D-serine after their initial placebo day (placebo/D-serine) or placebo after their initial D-serine day (D-serine/placebo) vs. those who received a second consecutive D-serine treatment (D-serine/D-serine). A significant difference was observed across orders, reflecting a significant D-serine effect ($p=0.044$).

Furthermore, following just two consecutive D-serine treatments, Sz outcomes for behavioral plasticity were normalized vs. controls ($p=0.36$). In prior studies, alterations in cognition were observed following ~50 hours of training^{61,66}. *Thus, a noteworthy result of this study is the observed large effect size improvement following only 2 weekly sessions paired with D-serine.*

Sz patients receiving two consecutive sessions of D-serine had a significantly larger pre-post change in MMN than those receiving placebo ($p=0.02$, $d=0.7$), demonstrating target engagement of D-serine. A relationship between plasticity and functional target engagement was demonstrated by a significant correlation between changes in MMN and plasticity improvements ($r=-0.34$, $p=0.034$).

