Aim #2 (R61): To confirm the functional relationship of auditory plasticity improvements. In prior studies, auditory plasticity deficits have been related to impairments in higher, functionally relevant auditory functions. *Hypothesis: We hypothesize that plasticity outcomes will be related to functionally relevant outcomes (auditory cognition³, primary), emotion recognition (AER)¹⁰, MMN, θ -ITC, other functional outcomes and pharmacodynamics.*

Aim #3 (R33): To evaluate effects of D-serine-enhanced auditory plasticity on auditory cognition. 60 Sz patients will be randomized to auditory remediation + D-serine or placebo. 16 sessions (1x week) of treatment will be utilized, with dose dependent on R61 results. *Hypothesis: We hypothesize that D-serine treated subjects will have greater improvements in auditory cognition³ than placebo. Plasticity, AER, MMN, θ -ITC, reading, other cognitive/functional measures and pharmacodynamics will be secondary outcomes.*

Inclusion/Exclusion Criteria

This section details your study sample(s) and addresses the requirement for risk minimization.

You may choose to divide your sample by population (healthy controls vs. subjects) or by procedure (subjects who will have an MRI) and then define different sets of criteria for each.

For each sample, create or insert a table to describe detailed criteria for study inclusion and exclusion and the method you will use to ascertain each criterion. The method of ascertainment may describe tests, scales and instruments. When relevant, indicate the level of training of the person who will make the assessment (e.g. clinical interview by a psychiatrist).

Inclusion/Exclusion Criteria needs to be numbered and listed in outline form (see Table template below).

CRITERION	METHOD OF ASCERTAINMENT
Inclusion:	
1. Age between 18-50	Self-report
2. DSM-V diagnosis of schizophrenia or schizoaffective disorder	SCID
3. Auditory Cognitive impairment demonstrated by: 1. MATRICS composite score (MCCB) composite domain score less than or equal to 0.5 standard deviation below normal (T score less than or equal to 45) 2. And at least one of the following: a. MCCB verbal memory domain score less than or equal to 0.5 standard deviation below	Screening MCCB

normal (T score less than or equal to 45) b. Tone matching score of less than or equal to 77.7%	
4. Willing to provide informed consent	Physician evaluation

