Provide a clear, concise narrative of study procedures with special attention to the subjects' involvement. Detail the overall study timeline and location of study procedures, list all interventions, assessments and interviews, estimate the duration of each procedure, provide dosing schedules, identify study personnel involved in each procedure, and provide credentials for relevant personnel. For complicated study designs, we strongly encourage attaching tables, flow-charts, and study algorithms.

In the R61, we will confirm target engagement of D-serine + auditory remediation, assess relationships of plasticity changes and cognition, safety and assess the optimal dose of D-serine treatment. In the R33, we conduct a randomized, placebo-controlled, parallel group study with the superior dose of D-serine combined with 16 weekly sessions of the same neuroplasticity-based auditory remediation. The structure of this grant requires successful completion of the R61 phase over 2 years prior to initiation of the R33 phase. We will amend the PSF and consent to include a full description of the R33 phase prior to its initiation.

The study will be conducted in groups of 15 subjects in which 12 subjects will receive D-serine for each of the three treatment visits and 3 will receive placebo for each of the three treatment visits. The first group of 15, will receive 80 mg/kg or placebo, and the second group of 15 subjects will receive 100 mg/kg or placebo, followed by a third group receiving 120 mg/kg or placebo. As previous studies noted minimal carry over effect of D-serine effects ([name] 2010), subjects may be permitted to participate in more than one phase with at least a six

month space in between.

If there are tolerability concerns at the 80 or 100 mg/kg doses, we will add a 60 mg/kg arm, ensuring the assessment of multiple doses. After each cohort, we will obtain permission from both the FDA and the IRB via an amendment, prior to the beginning of the next cohort. We require this safety milestone to be reached in order to begin the next cohort.

R61 Design (Table 1):

R61 Design	Table 1 (R61)	Baseline	Treatment Day			Follow-up ¹
			1	2	3	
		Day -30 to -1	Day 1	Day 8±2	Day 15±2	
	Consent	x				
	Medical screening	x				
	D-serine/Placebo		x	x	x	
	MMN		x	x	x	
	Auditory Remediation/EEG		x	x	x	
	Cognitive and behavioral ratings	x				
	Clinical laboratory/pregnancy/vitals	x	x	x	x	x
	SAFTEE/C-SSRS	x	x	x	x	x
	1. If necessary to follow-up any abnormalities.					

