Screening/Informed consent: Informed consent will be obtained before any study procedures, including screening procedures, are initiated. After providing informed consent, subjects will undergo full medical screening (medical history, physical examination, vital signs, laboratories for basic chemistries, blood counts, liver function tests, urinalysis, urine toxicology, serum pregnancy test for women, and thyroid tests, electrocardiogram [EKG]) and psychiatric screening (i.e., Structured Clinical Interview for DSM V Axis I Disorders (SCID) to confirm eligibility. Screening will occur over an up to 31-day screening period.

Baseline ratings: Eligible subjects will then undergo baseline cognitive and behavioral tests:

Randomization: Assignment to treatment groups will be on a random basis. Randomization will be stratified by baseline tone matching.

Auditory remediation visits: Subjects will then undergo three auditory remediation/EEG sessions. Each visit will follow the same format. Sessions are administered once a week±2 days. We utilize an auditory remediation program, in which participants are presented with paired tones (e.g. Stimulus 1 (“reference”) and Stimulus 2 (“test”): S1 and S2) and indicate which tone is higher in pitch (frequency). In the first pair, the ratio is 50% (e.g. 1000±500 Hz), and the difficulty level is adjusted to maintain a steady (~70% correct) level of performance across the 80 repeats. Ratios in each pair are log-transformed and averaged across 10-trial pairs (e.g., pairs 1-10, 11-20, etc.). When the reference (S1) remains constant (“fixed”), highly significant improvement is seen.

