Aim 1 Analysis: Aim 1 hypothesizes that D-serine will lead to greater plasticity, MMN, and theta-ITC changes than placebo, with the largest effect being seen at the 120mg/kg dose. Plasticity improvement (defined as change from trials 20 – 30 to trials 70 – 80 at end of session) in the 3rd week of treatment will be examined by using Cohen's d effect size estimates. Within each D-serine group, Cohen's d for within-subject change will be computed by taking the mean change in plasticity divided by the pre-treatment standard deviation. Similar Cohen's d values will be computed for the combined placebo group. Corresponding 95% confidence intervals (based on standard theory or constructed via bootstrapping if assumptions for constructing the confidence intervals based on parametric methods are not satisfied) will be computed. Similar procedures will be followed for assessing within-subject changes in MMN and theta-ITC. For each D-serine dose level, Cohen's d for between-group differences will be computed as (mean change for the D-serine group minus mean change for the placebo group) divided by standard deviation of the change scores in the combined placebo group.

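### Should the R61 cognition correlation be changed as a go/no-go item because cognition is measured only before dosing?

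*Protocol*

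**What the plan says.** Study overview (Protocol, Background, Significance, and Rationale) lists the engagement items and then adds "plus a moderate effect size correlation with functionally relevant cognitive measures", identified there as auditory cognition. Assessment Instruments gives the content: "auditory cognition is defined as the HVLT and letter number sequence test of the MCCB".

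Timing comes from Study Procedures. In Table 1 the row "Cognitive and behavioral ratings" has one mark, in the baseline column. The text agrees: "Eligible subjects will then undergo baseline cognitive and behavioral tests". The account of the treatment visits lists EEG, MMN, a D-serine level, laboratory tests and side-effect ratings, but no cognitive test.

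Plasticity is measured on drug. The SAP's Aim 1 Analysis takes the within-session change "at end of session) in the 3rd week of treatment will be examined", and its between-group effect size uses "mean change for the D-serine group minus mean change for the placebo group".

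Specific Aims and Hypotheses separates the two purposes. Aim 1 is target engagement and safety. Aim 2 is the functional relationship of plasticity, introduced with "In prior studies, auditory plasticity deficits have been related to impairments in higher, functionally relevant auditory functions". Study overview leaves functional improvement as an outcome to R33.

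The section Milestones and Rationale (Go/No-Go Criteria) names a plasticity-MMN relationship and does not mention cognition. Its list is introduced as non-exhaustive, and full detail is deferred to section 3C4 of the main application.

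**The concern.** A score taken before the first dose cannot respond to D-serine, so an inert drug can meet this item. Aim 2 itself reports that the association was already seen in earlier work. Because the item is joined to the others, a miss on it alone could stop R33 after D-serine had met every engagement item, and R33 is where cognition is to be tested as a treatment outcome.

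There is also a possible perverse case. The Background reports of the pilot that "Sz outcomes for behavioral plasticity were normalized vs. controls". If that reflected larger gains in the most impaired patients, treatment would flatten the relation between plasticity and baseline cognition, and an effective drug would be more likely to miss. At stake would be a useful treatment abandoned for a reason unrelated to whether it works.

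**Working it through.** **Inputs.** Each of three cohorts has 12 D-serine and 3 placebo patients: 3 × 12 = 36, 3 × 3 = 9, total 45. The supplied text gives no cut-off or power for the correlation, so there is no figure to reproduce. Assumptions: moderate means observed r ≥ 0.30; the correlate is week-3 plasticity, scored so that the expected sign is positive; n = 36 (D-serine only) or 45 (all).

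**1. Does the item do its own job?** By Fisher's z, P(pass) = 1 − Φ{[atanh(0.30) − atanh(ρ)] × √(n − 3)}, with atanh(0.30) = 0.3095.

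| True ρ | n = 36 | n = 45 |
|---|---|---|
| 0 | 0.038 | 0.022 |
| 0.30 | 0.500 | 0.500 |
| 0.40 | 0.744 | 0.770 |
| 0.50 | 0.916 | 0.940 |

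For example, at ρ = 0.40 and n = 45: (0.3095 − 0.4236) × √42 = −0.74, giving 0.770. A task unrelated to cognition rarely passes. One clearly related usually does.

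**2. What does a drug effect do to it?** Simulation (60,000 runs), with the same shift d (in SD) added to all 36 treated patients and all 45 pooled:

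| True ρ | Inert | d = 0.5 | d = 0.8 |
|---|---|---|---|
| 0.30 | 51.0% | 48.9% | 46.6% |
| 0.40 | 78.0% | 76.1% | 73.1% |

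In D-serine patients alone at ρ = 0.30 it is 51.0% with or without the shift. The ratio of effective to inert is 46.6/51.0 = 0.91 and 73.1/78.0 = 0.94. The item is nearly neutral about the drug.

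**3. Where does the drug information come from?** Take the SAP's between-group effect size with a cut-off of 0.5. For 36 against 9 it passes 10.8% (inert), 51.9% (true d = 0.5) and 78.8% (d = 0.8), ratios of 51.9/10.8 = 4.8 and 78.8/10.8 = 7.3. For 12 against 9 it passes 14.5%, 51.2% and 75.0%, ratios of 3.5 and 5.2. If the two items are treated as independent (an assumption), adding the correlation changes 7.3 to about 7.3 × 0.91 = 6.6. The rule still separates an effective drug from an inert one.

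**4. The perverse case.** At ρ = 0.30, d = 0.8 and n = 45, lowering the treated slope by 0.2 cuts the pass rate from 46.6% to 13.5%. Raising it by 0.2 lifts it to 80.7%. The documents support neither direction: the pilot statement is a group-level comparison with controls.

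**5. Sensitivity to the cut-off.** Inert drug, ρ = 0.30, n = 45: 67.1% at r ≥ 0.24 (the equivalent of d = 0.5, from 0.5/√4.25) and 6.2% at r ≥ 0.50.

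**6. Would a softer stop rule be better?** Suppose R33 stops only when the upper 95% limit for a dose-adjusted r is below 0.30. On the z scale, the stop requires:
- n = 36, two dose terms: below 0.3095 − 1.96/√31 = −0.043, so r below about −0.04.
- n = 45, three group terms: below 0.3095 − 1.96/√39 = −0.004, so r below about −0.004.

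A moderate-correlation milestone becomes a requirement that r not be negative. In simulation the chance of a stop at ρ = 0.30 falls to 2.4%, but at ρ = 0 it is only 40.4% (n = 36) or 48.9% (n = 45). The pass ratio for ρ = 0.30 against 0 drops from 0.509/0.042 = 12 and 0.511/0.027 = 19 to 0.976/0.596 = 1.6 and 0.976/0.511 = 1.9.

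The sign also matters. The Background reports plasticity correlations with MMN and theta-ITC as negative (−0.34 and −0.39). If cognition runs the same way and the sign is not fixed, a true r of −0.3 (n = 36) would trigger the stop with probability Φ[(0.3095 − 0.043) × √31] = 0.93.

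**The case for a change.** The strongest case for a change is that a relevance check should not carry a veto. At a true correlation of 0.30 the item misses about half the time, and at 0.40 about a quarter (23% with 45 patients, 26% with 36), whatever the drug does. The MCCB entry limit may narrow the range of cognition and push r lower still. R33 would answer the functional question directly.

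Much of this stands. The item adds risk of a stop if it binds, and a pass is not evidence that D-serine improves cognition or that plasticity gains go with cognitive gains.

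Three things limit it:
- A miss rate near 50% is what any point cut-off gives when the truth equals it. The effect-size item does the same, at 51-52% passing for a true d of 0.5.
- Requiring evidence of functional relevance before a 16-session trial is a legitimate choice for sponsor and funder, and item 1 of the working shows that the correlation supplies such evidence.
- Repeating the two tests after session 3 would let the item see a cognitive change, but the Background says earlier cognitive change followed about 50 hours of training. The protocol's own dose-escalation work did show MCCB gains, after 4 to 6 weeks of daily dosing rather than three weekly doses.

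**Conclusion.** No change to the plan follows. The pre-dose timing is real and consistent across Table 1, the Study Procedures text and Assessment Instruments, but it suits Aim 2, which asks whether plasticity relates to functionally relevant cognition. Drug effect is judged by the plasticity, MMN and theta-ITC items. Under a uniform drug effect the correlation is almost neutral (ratios 0.91-0.94 at d = 0.8), and it separates a related task from an unrelated one (74-77% against 2-4% passing). Keeping it as a milestone is a fair trade-off: protection against pursuing an irrelevant task, at the price of some stops when the true correlation is near the cut-off.

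These sizes rest on a cut-off of 0.30, week-3 plasticity as the correlate and 36 or 45 patients. The supplied text fixes none of them, and the supplied SAP stops within Aim 1. The milestones section leaves cognition unnamed and defers to the main application, so whether the item binds cannot be settled here. The correlate, sign and analysis set are details that analysts can take from that application. The result should be read as a relation with baseline cognition and no more.
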